8.0 Statistical Considerations

General

This will be a two-arm Phase II trial of eltrombopag in patients receiving an allogeneic stem cell transplant. One arm will be for patients receiving cord blood, and the other will be for patients with haploidentical donors. The primary objective of the trial will be to estimate the rate of platelet engraftment by Day 60 in patients undergoing cord blood transplant (CBT) or haploidentical donor stem cell transplantation treated with eltrombopag. We will use a dose of 300 mg/day for 60 days in each arm. With no dose increase, we originally planned to enroll a minimum of 20 patients and a maximum of 30 patients in each arm, and the total accrual for the study would have been no more than 60 patients. In October 2015, because the vast majority of patients accrued have entered the haploidentical arm, the study was modified to allow for up to 20 additional patients (for a total of 50) in this arm. In January 2016, the protocol will be further modified to allow for up to 55 patients in the haploidentical arm. The protocol will still enter a maximum of 60 patients total. When registering patients in CORe, treatment arm assignment will be designated.

Primary Endpoint: Sample Size Justification

Historical data for cord blood transplants at MDACC indicates that approximately 44% of patients experienced platelet engraftment of $> 50K/\mu L$ by Day 60. We expect to increase this to at least 71% in this trial with the addition of eltrombopag. With 20 patients in the cord blood arm, we will have 80% power to detect an increase to 71%, assuming a one-sided exact binomial test with a 5% Type I error rate. Only patients who complete treatment without missing the drug for more than 10 days will be included in this analysis, although patients who are removed because of high platelet count will be counted as successes. We expect that 80% of patients will be evaluable for the primary endpoint under these criteria. If we enroll more than 20 patients in this arm, we will have greater power to detect this increase. As discussed above, we now (October 2015) expect fewer than 20 patients to enter this arm. We accept that this arm will be underpowered to detect the specified difference.

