1.0 Objectives

Primary Objective: To estimate the rate of platelet engraftment by Day 60 in patients undergoing cord blood transplant (CBT) or haploidentical donor stem cell transplantation treated with eltrombopag.

Secondary objectives:

- 1) To assess safety of eltrombopag in this population
- 2) To assess neutrophil engraftment with eltrombopag in this population
- 3) To characterize immune reconstitution
- 4) To assess overall survival (OS)
- 5) To assess progression free survival (PFS)
- 6) To assess incidence of acute graft-versus-host disease (GVHD)

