Likewise platelet engraftment is delayed occurring at a median of 28 days (0-395 days) in patients undergoing haploidentical transplantation using T replete marrow graft with post-transplant cyclophosphamide.^[10] This is likely due to use of bone marrow as a graft source and use of cyclophosphamide after transplant, which results in significantly delayed engraftment. A major cause of mortality in these patients is infection resulting from poor immune reconstitution.^[2,7,14] Further effort at improving engraftment and immune reconstitution is clearly needed.

At MD Anderson Cancer Center, we have previously reported engraftment data in a smaller number of patients in both of these groups.^[15-18] In order to get detailed data for engraftment in a larger number of patients and to serve as a baseline for this proposal, we reviewed our historic platelet engraftment data in these two groups of patients and they are summarized in Table 2.

Table 2

	Cord blood (n=91)	Haploidentical Donor (n=54)
Time to platelet >20K Median (range) days	43 (0-126)	29 (0-59)
At Day 30 proportion of patients with		
Platelet >20K	19%	61%
Platelet >50K	2%	20%
At Day 60 proportion of patients with		
Platelet >20K	60%	88%
Platelet >50K	44%	63%

Hence at Day 30 after transplant only 2% (2/91) of patients receiving cord blood and only 20% (11/54) of patients receiving haploidentical graft achieved platelet count greater than 50,000/ μ l. We wish to improve these results in the current study.

Rationale for eligibility criteria and study design

We would like to include as many patients as possible therefore all patients receiving cord blood or haploidentical transplant treated on any protocol will be eligible for this study. Following exceptions are made for safety concerns.

- a) Patients with liver dysfunction are excluded from this study because the drug exposure is higher in patients with severe liver dysfunction and modest hepatic toxicity was observed in few patients in previous clinical trials of this drug. Likewise patients with renal dysfunction are excluded as limited data are available in the setting of kidney failure.

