5.0 Treatment Plan

Dosage and Administration:

For inpatients: documentation of drug administration will be on the medication administration record (MAR).

For outpatients: patients will be given a pill diary to record dose taken, missed, or vomited.

Dose may be repeated if the patient vomits within 30 minutes of taking the drug.

1. Eltrombopag will be given as a single daily dose of 300mg orally on an empty stomach (1 hour before or 2 hours after a meal) for 60 total days.
2. Eltrombopag will be started on Day -1 (the day prior to stem cell infusion in cord blood patients) and Day +5 in patients receiving haploidentical transplant.
3. If for any reason patient is unable to take oral drug, number of days missed and reason will be documented.
4. Allow a 4-hour interval between eltrombopag and other oral medications/supplements containing polyvalent cations, such as iron, calcium, aluminum, magnesium, selenium, and zinc.
5. Drug will be stopped and not resumed:
 - a) if at any time platelet count is $\geq 250 \times 10^9/l$, or
 - b) after completing 60 days of treatment, or
 - c) at patient request, or
 - d) per PI discretion if patient misses more than 10 consecutive doses of drug,

or

- e) if it is deemed unsafe and detrimental to patient health by the treating physician or the principal investigator.

6. Patients will be taken off the study:
 - a) at patient request, or
 - b) if it is deemed unsafe and detrimental to patient health by the treating physician or the principal investigator based on CTCAE Version 4.0 toxicity grading, or
 - c) 1 year after drug initiated.

Unused and/or expired drug will be disposed per institutional policy.

Concomitant medications will be documented in the medical record but will not be entered into PDMS/CORE. These medications are considered standard of care and have no scientific contributions to the protocol, therefore no data will be captured on the various medications needed or their side effects.

The use of medications that cause thrombocytopenia is permitted if needed, at the discretion of the patient's physician.

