7.0 Evaluation During The Study

The required lab tests and time points are part of the standard post-transplant care.

1. Following lab studies will be done daily until neutrophil engraftment and then at least once a week during active treatment period and for 4 weeks after completion of eltrombopag: CBC, Na, K, Cl, CO2, BUN, Creatinine.
2. Liver function tests, Bilirubin, Alkaline Phosphatase and ALT will be done weekly during active treatment period and for 4 weeks after completion of eltrombopag.
3. Total number of red cell and platelet transfusion given will be collected during active treatment period.

Correlative Studies

Thrombopoietin acts on early stem cells and progenitor cells. Eltrombopag was shown to increase not only platelets but also white cells and hemoglobin. It is possible that it may impact recovery of immune system after transplant.^[19,43,45] We will therefore do immune reconstitution studies at various time points and compare it to historical control to assess impact of Eltrombopag on immune recovery. Samples will be sent to [name]

laboratory at MD Anderson for analysis.

Required: Immune reconstitution studies on peripheral blood (70 mL) will be done on Day 30 (± 7 days), 60 (± 7 days), 90 (± 10 days), 180 (± 30 days), 365 (± 30 days).

Optional: Immune reconstitution studies on bone marrow (5 mL) will be done on Day 30 (± 7 days) and Day 90 (± 10 days).

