Secondary endpoints in the trial include platelet engraftment > 20K/ μ l at Day 60, platelet engraftment > 20K/ μ l and > 50K/ μ l at Day 30, neutrophil engraftment, the time to platelet and neutrophil engraftment, overall survival (OS), progression free survival (PFS), the cumulative incidence of acute and chronic graft vs. host disease (GVHD), and toxicity. Neutrophil engraftment is defined as the first of three consecutive days that the ANC is > 0.5 k/ μ L.

We will estimate the cumulative incidence of each of the engraftment parameter with death or relapse as a competing risk. Neutrophil and platelet engraftment will be recorded as per our departmental standard practice.

For survival parameters, we will use the method of Kaplan and Meier to estimate the distribution of survival times, and we will compare distributions using the log-rank test. We will use Cox proportional hazards regression methods to model survival parameters as a function of disease and demographic covariates of interest. We will use the method of Gooley et al to estimate the cumulative incidence of GVHD. We will use logistic regression to model the association between engraftment endpoints and covariates of interest. Analyses will be performed separately by arm (cord blood or haploidentical).

We will provide descriptive summaries of toxicity by arm and dose and immune recovery parameters at various time points.

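### Every removal for a high platelet count is scored as a primary success, with no requirement that the count reflects engraftment or falls by Day 60

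*Combined protocol and SAP*

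**What the plan says.** The primary objective in 1.0 is "To estimate the rate of platelet engraftment by Day 60 in patients undergoing cord blood transplant (CBT) or haploidentical donor stem cell transplantation treated with" the study drug. Section 8.0 uses a threshold of more than 50K/µL. For the cord arm it says "Historical data for cord blood transplants at MDACC indicates that approximately 44% of patients experienced platelet engraftment of" more than 50K/µL by Day 60, and "We expect to increase this to at least 71% in this trial with the addition of eltrombopag". For the haploidentical arm the benchmark is 63% and the target 88%.

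For both arms, 8.0 limits the primary analysis to patients who complete treatment with no more than 10 days of missed drug, "although patients who are removed because of high platelet count will be counted as successes". It then says that patients with graft failure are replaced.

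Section 5.0 item 5a stops the drug permanently "if at any time platelet count is" at least 250 × 10⁹/L. Item 2 starts dosing on Day -1 in the cord arm and Day +5 in the haploidentical arm, and item 1 gives 60 days of treatment. The eligibility criteria in 4.1 and 4.2 set no platelet limit.

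On how platelet engraftment is determined, the only text is under Secondary Endpoints in 8.0: "Neutrophil and platelet engraftment will be recorded as per our departmental standard practice". That practice is not described. Neutrophil engraftment, by contrast, has a stated three-consecutive-day definition. On transfusions, 7.0 item 3 says: "Total number of red cell and platelet transfusion given will be collected during active treatment period".

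**The concern.** The high-count clause is a scoring rule of its own. It does not refer to the engraftment definition, to the graft having been infused, or to Day 60. A patient can therefore become a primary success by a route that need not measure the thing being estimated.

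Two routes follow from the dosing schedule. In the cord arm, drug is given from the day before infusion, so a qualifying count at the start can only be the patient's own platelets. In the haploidentical arm, dosing continues a few days past Day 60, so a stop in that period would be scored as an event by Day 60. The clause also sits beside the graft-failure replacement rule with no order of precedence: the same patient could be a success under one sentence and replaced under another.

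A false success raises the observed rate, which is the direction of the hoped-for effect. Because the primary objective is to estimate this rate, the main result is affected whatever the test shows.

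**Working it through.** **Inputs.** Benchmarks 44% and 63%, targets 71% and 88%, n = 20 per arm, one-sided exact binomial test at 5%, 80% of patients evaluable, up to 55 haploidentical patients (all 8.0). Dosing start days, 60-day duration and the 250 × 10⁹/L trigger (5.0).

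**The plan's own power figures.**
- Cord, n = 20: the smallest rejection count is 13. P(X ≥ 13 | 0.44) = 0.048 and P(X ≥ 13 | 0.71) = 0.802.
- Haploidentical, n = 20: the smallest rejection count is 17. P(X ≥ 17 | 0.63) = 0.030 and P(X ≥ 17 | 0.88) = 0.787.

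The stated 80% reproduces for cord and is within two points for haploidentical. The power arithmetic is not the issue.

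**Dosing windows (60 consecutive days).**
- Cord: Day -1 + 59 = Day +58.
- Haploidentical: Day +5 + 59 = Day +64, so Days 61 to 64 lie after the endpoint window.

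**The rules applied literally.**
- A cord patient has a count of 250 × 10⁹/L or more on Day -1. Drug stops for good (5.0 item 5a), and 8.0 scores a success before the graft could contribute.
- The same patient later has graft failure. One sentence of 8.0 says success and another says replace. Nothing says which prevails.
- A haploidentical patient first reaches 250 × 10⁹/L on Day +62. Section 8.0 scores a success by Day 60. Such a patient may have passed 50K earlier and be a success anyway, but the clause does not ask.

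**Size per case.** If the patient would otherwise be a failure, each case adds 1/n to the observed rate.
- Cord: 1/20 = 5.0 points, and more if fewer are evaluable. Section 8.0 now expects fewer than 20 cord patients.
- Haploidentical: 0.80 × 55 = 44 evaluable, and 1/44 = 2.3 points.

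**Hypothetical effect on the test.** Let m be the share of true failures scored as successes, with the benchmark unaffected. The success probability under the null becomes p0 + m(1 − p0). The documents give no value for m; 5% and 10% are assumed.
- Cord, n = 20, 13 or more successes: m = 0, 5%, 10% gives success probabilities 0.440, 0.468, 0.496 and false-positive rates 4.8%, 8.0%, 12.4%.
- Haploidentical, n = 44, 34 or more successes: 0.630, 0.6485, 0.667 and 3.2%, 5.5%, 8.9%.

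**The case against.** The strongest reply is that departmental practice already handles this, and that Table 2 in 2.0 shows it does. The row "Time to platelet >20K Median (range) days" gives a cord median of 43 days. Only 19% of cord patients were above 20K at Day 30, and only 2 of 91 were above 50K. A median that late is hard to square with routine scoring of host or transfused counts. Even if both of those patients were false successes, 2/91 = 2.2% of patients, or 2.2/56 = about 4% of those not engrafted by Day 60, is below the lowest misclassification rate assumed above. Table 2 also labels its proportions as at Day 60. If that is a snapshot, an early count could not enter the benchmark at all.

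This largely answers a stronger reading that a reader might infer: that the ordinary >50K route also counts host or transfused platelets. The Table 2 ranges do start at day 0 in both groups, but that shows only that at least one patient per group was so recorded, at >20K rather than at the primary threshold. The documents state no nadir or transfusion-free condition; they do not show that the departmental practice lacks one.

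Two further points stand. Section 5.0 lists the 250 × 10⁹/L count as a reason to stop drug, not to leave the study, so tying it to removal in 8.0 is an inference, although no other high-count rule exists. And 7.0 gives no start day for daily blood counts, so only dosing, not daily testing, is known to begin on Day -1.

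The reply does not reach the high-count clause. The departmental-practice sentence sits under Secondary Endpoints and does not qualify it, and nothing indicates that the historical rates used such a clause. Any cancellation against the benchmark is therefore not assured.

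**Conclusion.** The point holds for the high-count clause. As written, it can score a pre-graft host count, or a stop after Day 60, as platelet engraftment by Day 60, and it conflicts with the graft-failure replacement rule. This rests on reading removal in 8.0 as the stop in 5.0 item 5a. Whether the >50K route shares the problem is not known, because the definition is not written down.

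The frequency is also unknown and may be low. What can be stated is the effect per case: at least 5 points in a cord arm of 20 or fewer, and about 2.3 points with 44 haploidentical patients, for a patient who would otherwise be a failure. The pre-infusion route applies to the cord arm only; with uninterrupted dosing, the post-Day 60 route applies to the haploidentical arm only.

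A reader might take the rise from 4.8% to 8.0% or 12.4% as the trial's actual error rate. The documents do not support that: the figures assume 5% or 10% misclassification, an unaffected benchmark and 20 evaluable cord patients, which 8.0 no longer expects. Nor do the documents show that a transfusion-free condition is uncheckable: 7.0 collects totals only, but transfusion dates should be obtainable from existing records. The change is worth making because it is cheap and protects the primary estimate.

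**What to change.** In 8.0:
- Write out the departmental definition of platelet engraftment above 50K/µL, including its post-nadir and transfusion-free conditions. It must be workable with blood counts that may be only weekly after neutrophil engraftment (7.0 item 1).
- Count a removal for high platelet count as a success only if the patient meets that definition on or before Day 60. Otherwise score the patient on later counts through Day 60.
- Name 5.0 item 5a as the trigger, if that is what is meant.
- State which rule prevails when graft failure follows a high-count stop.
- Confirm that the 44% and 63% benchmarks follow the same definition and the same reading of Day 60, or recompute them.

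In 7.0 item 3, add platelet transfusion dates, taken from existing records, so that the condition can be checked.

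The cost is protocol wording, some record abstraction, and possibly a re-tabulation of Table 2. The reported rate may come out slightly lower. Dosing and the drug-stopping rule are not changed.

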Secondary endpoints in the trial include platelet engraftment > 20K/ μ l at Day 60, platelet engraftment > 20K/ μ l and > 50K/ μ l at Day 30, neutrophil engraftment, the time to platelet and neutrophil engraftment, overall survival (OS), progression free survival (PFS), the cumulative incidence of acute and chronic graft vs. host disease (GVHD), and toxicity. Neutrophil engraftment is defined as the first of three consecutive days that the ANC is > 0.5 k/ μ L.

We will estimate the cumulative incidence of each of the engraftment parameter with death or relapse as a competing risk. Neutrophil and platelet engraftment will be recorded as per our departmental standard practice.

For survival parameters, we will use the method of Kaplan and Meier to estimate the distribution of survival times, and we will compare distributions using the log-rank test. We will use Cox proportional hazards regression methods to model survival parameters as a function of disease and demographic covariates of interest. We will use the method of Gooley et al to estimate the cumulative incidence of GVHD. We will use logistic regression to model the association between engraftment endpoints and covariates of interest. Analyses will be performed separately by arm (cord blood or haploidentical).

We will provide descriptive summaries of toxicity by arm and dose and immune recovery parameters at various time points.

9.0 Adverse Events and Reporting Requirements

9.1 Grading assessment

The severity of the adverse events (AEs) will be graded according to the Common Terminology Criteria v4.0 (CTCAE). Adverse events and protocol specific data will be entered into PDMS/CORe. PDMS/CORE will be used as the electronic case report form for this protocol.

9.2 Causality Assessment

For the purpose of this study events known to be caused by Eltrombopag will be assessed as definitely related.

Events known to be caused by components of the transplant package and its direct consequences as well as those events known to be related to drugs used for the treatment of GVHD, infections and supportive treatment will be scored as unrelated. When the relationship of the adverse event cannot be ruled out with certainty the AE may be considered possibly related.

The PI will be responsible for assessing the causality and will be final arbiter. Documentation of grade, onset/resolution date and attribution will be entered into the patient's medical record and signed by the PI.

9.3 Collection of adverse events

Only those events known to be caused by Eltrombopag will be recorded in the designated case report form (PDMS/CORE). Collection of adverse events will reflect the onset and resolution date and maximum grade. Intermittent events should be labeled as such and followed until resolution. If a patient is taken off study while an event still ongoing, this will be followed until resolution unless another therapy is initiated.

Events known to be caused by components of the transplant package and its direct consequences as well as those events known to be related to drugs used for the treatment of GVHD, infections and supportive treatment will not be collected in the designated case report form/database. Concurrent medications considered standard of care for transplant patients will not be captured in the case report form. They will be documented in the medical record.

Adverse events related to the study drug will be collected and recorded for the duration of active treatment plus 30 days.

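### Read literally, section 9.3 keeps possibly related adverse events off the case report form, and section 8.0 does not say which attribution levels or data source its toxicity stopping rule uses

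*Combined protocol and SAP*

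**What the plan says.** Five places in the combined protocol and SAP bear on this.

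- **9.1 Grading assessment** names the database: "Adverse events and protocol specific data will be entered into PDMS/CORe", and "PDMS/CORE will be used as the electronic case report form for this protocol". It sets no attribution limit.
- **9.2 Causality Assessment** defines the classes. Definite: "For the purpose of this study events known to be caused by Eltrombopag will be assessed as definitely related". Unrelated: events known to come from the transplant package, or from drugs for GVHD, infection or supportive care. Possible: "When the relationship of the adverse event cannot be ruled out with certainty the AE may be considered possibly related". On who decides: "The PI will be responsible for assessing the causality and will be final arbiter". Grade, dates and attribution go into the medical record over the PI's signature.
- **9.3 Collection of adverse events** opens with "Only those events known to be caused by Eltrombopag will be recorded in the designated case report form (PDMS/CORE"). Its second paragraph says that events known to have a transplant or supportive-care cause "will not be collected in the designated case report form/database". It closes with "Adverse events related to the study drug will be collected and recorded for the duration of active treatment plus 30 days".
- **8.0, Safety Monitoring Rule** follows drug-attributable non-hematologic toxicity of grade 4 or above up to Day 60, separately by arm. It does not map attributable onto the 9.2 classes and names no data source. **8.0, Secondary Endpoints** promises descriptive toxicity summaries by arm.
- **9.6 Reporting Requirement** sends all serious adverse events to the IND Office whatever their attribution.

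**The concern.** The opening sentence of 9.3 reuses the phrase by which 9.2 defines definitely related events, and puts *only* in front of it. Taken together, the two sections admit the definite class to the form and leave the possible class out.

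That class matters in this population. Recipients of cord blood or haploidentical grafts have many competing causes of severe toxicity, so events that cannot be assigned with certainty would be scored there. Safety is the first secondary objective, and there is no concurrent control arm to show an excess that attribution has missed. If the summaries are built from the form, toxicity whose link to the drug is uncertain does not appear in them. If the stopping rule is also run from the form, and is meant to cover possibly related events, it works on too low a count.

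**Working it through.** **Step 1. What each passage does with a possibly related event**

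| Place | Treatment of the event |
|---|---|
| 9.1 | Adverse events go into the form; no limit stated |
| 9.2 | Separate class; attribution documented in the medical record |
| 9.3, first sentence | Not admitted, if *known to be caused* means what 9.2 says |
| 9.3, exclusion paragraph | Not excluded; only events with a known other cause are |
| 9.3, last sentence | Collected, if *related* includes possibly related |
| 8.0 | Undetermined; no attribution level and no source |
| 9.6 | Reported to the IND Office if serious |

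Within 9.3 the class is neither clearly admitted nor excluded by name, and the only sentence that defines what goes on the form leaves it out.

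**Step 2. Two readings of *known***

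- *The 9.4 list of expected events.* Thrombosis, stroke symptoms, abnormal liver tests and the other listed events are recorded. Only unlisted possibly related events are left out, so the gap is small.
- *Certainty in the individual case.* A listed event with a competing transplant cause could also be left out, so the gap is larger.

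The documents do not choose between these and give no share of events in either class.

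**Step 3. Reproduce the stopping rule**

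Inputs, all from 8.0: prior Beta(0.4, 1.6), limit 0.20, cutoff 0.95, maximum 55 patients per arm. With x events in n patients, stop if Pr(θ > 0.20) > 0.95 under Beta(0.4 + x, 1.6 + n − x). An exact binomial recursion with looks after patients 1 to 54 gives:

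| True rate | 5% | 10% | 15% | 20% | 25% | 30% | 35% | 40% |
|---|---|---|---|---|---|---|---|---|
| Stopping probability | .003 | .017 | .063 | .188 | .425 | .696 | .887 | .971 |

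All eight equal the printed values.

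**Step 4. Sensitivity to incomplete counting (illustration only)**

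The rule responds to the rate of events counted: counted rate = true rate × share counted. The shares below are assumptions; none comes from the documents. The table also assumes that the rule is run from the form and that possibly related events belong to its target.

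| Share counted | True 40% | True 30% | True 25% |
|---|---|---|---|
| 100% | .971 | .696 | .425 |
| 95% | .948 (counted .38) | .619 (.285) | .357 (.2375) |
| 90% | .911 (.36) | .537 (.27) | .295 (.225) |
| 75% | .696 (.30) | .295 (.225) | .147 (.1875) |
| 50% | .188 (.20) | .063 (.15) | .034 (.125) |

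Solving for the counted rate, the stopping probability is .90 at .355 and .50 at .2635. At a true rate of 40% these correspond to shares of .355/.40 = 89% and .2635/.40 = 66%. At that rate a loss of a few percent costs the rule little, whereas a loss of a third or more takes it below an even chance of stopping.

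**The case against.** **9.1 does not contradict 9.3.** It sits under grading and names the scale and the database; 9.3 sets the scope of collection. A specific section may narrow a general one. This stands, and 9.1 should not be counted as a firm contradiction.

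**The last sentence of 9.3 mainly sets a time window.** It does not name the form, and the 9.4 heading uses *related* for expected drug effects. This also largely stands. It weakens the conflict within 9.3 but leaves the literal *only* in force, so the omission remains.

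**Definite-only capture may be intended.** In transplant recipients on many drugs it is a coherent plan. If so, the rule works on its target and loses no operating characteristic, but 8.0 should state that narrower target. The summaries would still omit possibly related toxicity.

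**The capture shares have no source.** Correct. Step 4 shows sensitivity and estimates nothing about this trial.

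**The data exist elsewhere.** They do: attribution is in the PI-signed medical record and serious events reach the IND Office. However, no passage ties either source to the rule or the summaries, and a grade 4 event need not meet the definition of serious.

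**Stronger readings.** A reader might infer that drug toxicity goes unrecorded, that the stopping rule is disabled, or that patients are unprotected. The documents support none of these. They do not say that the rule runs from the form, they keep the events in other records, and the patient-level provisions for stopping treatment in 5.0 do not depend on the form.

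**Conclusion.** The concern holds as a defect in the scope of data collection. Because 9.2 equates *known to be caused* with definitely related, 9.3 followed literally keeps possibly related events off the case report form, and toxicity summaries built from it would understate them. The effect on the stopping rule is conditional on the rule being run from the form and on *attributable* including possibly related events.

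The size cannot be determined from the documents. It is small on the 9.4-list reading and larger on the individual-certainty reading. Nothing shows that events were in fact missed. This is a cheap improvement of minor to moderate priority.

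**What to change.** **In 9.3**, change the first sentence so that every event scored possibly or definitely related is recorded in PDMS/CORE with its attribution, and align the last sentence with it. The minimum is all such non-hematologic events of grade 4 or higher, but stopping there would still leave lower-grade possibly related events out of the summaries.

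**In 8.0**, report toxicity by attribution level. State which 9.2 classes count as attributable to the drug and which source feeds the rule, for example the PI-signed attributions cross-checked against the serious adverse event reports. The trial team should choose the level. If possibly related events are to count, the team should confirm that the 20% limit suits the broader event. The printed operating characteristics already depend on the counted rate, so they need re-running only if the limit, prior, cutoff or maximum sample size changes.

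**Cost.** Wording in two sections and a modest number of extra form entries. If possibly related events are counted, stopping for transplant-caused events becomes more likely: the protocol's own table gives .188 at a counted rate of 20% and .425 at 25%. Recording events with their attribution does not commit the team to counting them and keeps both definitions available.
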